
On February 12, 2016, the treatment phase for the first cohort of randomized participants at the UCD site (5 Leukine treated at the $250\ \text{mcg}/\text{m}^2/\text{day}/\text{SQ}$ and 5 placebo controls) was completed, in addition to 3 randomized participants from the USF site who had completed the trial. The DSMB

reviewed the data for all of these participants and recommended the following changes to the protocol going forward:

- “1) Based on review of the safety data reported to the DSMB, the current study dosing protocol does not present safety concerns and we have no recommended changes to dosing.
- 2) We recommend that the investigators establish specific criteria for terminating subjects from the study due to uncontrolled hypertension, in order to ensure standardized practices across subjects and treatment groups.
- 3) We recommend that with all scheduled DSMB data reviews in the future, the following data be included for review: 1) all vital sign data for each participant, 2) location of injection sites for each treatment and recorded outcomes from injection site review at each treatment visit, and 3) a tabulated list of the dates of treatment for each participant.
- 4) We request a copy at this point in time of the randomization assignment procedure currently being used by the University of Colorado site.
- 5) We recommend against altering the randomization procedure in any manner unless a protocol amendment with justification is approved by the IRB. This recommendation is prompted by the discovery that an investigator requested that the randomization assignment given to an enrolled participant who withdrew from the study be given to the next consecutively enrolled participant (i.e. that the same study drug be assigned to the next participant as had been given to the subject who withdrew).
- 6) The current protocol has no additional blood draws for complete blood count with differential (CBC with diff) beyond treatment day 15. We recommend a protocol change to include an additional CBC with diff on follow up day 90, at the same time as the day 90 scheduled blood draw for biomarkers and comprehensive metabolic panel. We recommend this change for all participants currently enrolled who have not reached day 90 as of April 7, 2016.

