Effects of Leukine[®] on mobilization of white blood cells will be determined by CBC with differential at screening, baseline Day 1 and on days 4, 6, 9, 11 and 15 of the treatment schedule (i.e. placebo or Leukine[®] at 250 mcg /m²/day/SC for 5 days/ week for three weeks), and at the 45 and 90 day follow-up visits. Vital signs, injection site review, and adverse event monitoring will be performed at each treatment visit. Complete metabolic panels (CMP) will be performed at screen, and on days 4, 9, 15, 45, and 90 days after initiation of GM-CSF treatment (Table 1 below summarizes the time-table of procedures for the entire study). The follow up MRI at the end of the treatment phase will provide information on any adverse changes in the brain, such as vasogenic edema and microhemorrhage. The DSMB will review all available data after each group of 5 Leukine[®]-treated and 5 placebo subjects have finished the treatment phase and determine whether the remainder of the subjects (5 Leukine[®]-treated and 5 placebo) will continue to receive the same full recommended dose (250 mcg/m²/day/SC).

HYPOTHESIS 1. Recombinant human GM-CSF, Leukine[®], will be tolerated by, and safe to use in mild-to-moderate AD patients.

SPECIFIC AIM 2. To test the hypothesis that Leukine[®] treatment will improve cognition in mild-to-moderate AD patients (*Secondary Endpoint*).

A battery of cognitive tests will be performed at baseline and at approximately 15, 45, and 90 days after initiation of Leukine[®] treatment to determine whether any AD features reverse during or after Leukine[®] treatment compared to subjects receiving placebo. Primary cognitive tests will include the Mini Mental State Examination (MMSE) and the ADAS-cog (Alzheimer's Disease Assessment Scale-cognitive subscale).

HYPOTHESIS 2. Leukine[®] treatment in adults with mild-to-moderate AD will improve cognition as measured primarily by MMSE total score and ADAS-cog total score.

SPECIFIC AIM 3. To investigate whether Leukine[®] treatment has an effect on Medial Temporal Lobe Atrophy (MTA) in mild-to-moderate AD patients (*Tertiary Endpoint*).

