For the indication of Leukine[®] in the acceleration of myeloid recovery in patients undergoing allogeneic BMT from HLA-matched related donors (<http://www.leukine.com/hcp-leukine-in-allogenic-bone-marrow-transplantation>), Leukine[®] was found to be safe and effective in accelerating myeloid engraftment, reducing the incidence of bacteremia and other culture positive infections, and shortening the median duration of hospitalization. In a multi-center, randomized, placebo-controlled, and double-blinded study, a total of 109 patients (53 Leukine[®], 56 placebo) were enrolled to evaluate the safety and efficacy of Leukine[®] for promoting hematopoietic reconstitution following allogeneic BMT. Hypertension was reported in 18 subjects receiving Leukine[®] (34%), and in 18 of the placebo subjects (32%).

On Sanofi's website under Important Safety Information for Leukine[®] (sargramostim), it is stated that "*Leukine[®] should be used with caution and monitored in patients with preexisting fluid retention, pulmonary infiltrates, or congestive heart failure, respiratory symptoms or disease; cardiac symptoms or disease; and renal or hepatic dysfunction.*" Sanofi's website states specifically for Cardiovascular Symptom that "*Occasional transient supraventricular arrhythmia has been reported in uncontrolled studies during Leukine[®] administration, particularly in patients with a previous history of cardiac arrhythmia. However, these arrhythmias have been reversible after discontinuation of Leukine[®]. Leukine[®] should be used with caution in patients with preexisting cardiac disease.*"

Due to safety concerns regarding the potential of cardiac symptoms or disease, the Co-Principal Investigator and/or the DSMB may determine that a trial subject should no longer remain in the trial if there is evidence of uncontrolled hypertension. For an individual who has consented to volunteer for the trial, meets inclusion criteria and is enrolled, then begins the treatment phase of the trial, but who subsequently is determined to exhibit uncontrolled hypertension, the DSMB will be immediately notified, adverse events reporting protocols will be followed, and the following criteria will be used to determine whether the subject needs to be removed from the trial:

Inclusion Screening Criteria for hypertension:

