- Should the potential subject have a screening blood pressure (BP) of more than 150 systolic or 95 diastolic, they will need to be under the care of a primary care provider for management of hypertension.
- The BP will have been well-controlled on a stable regimen for at least two months prior to study entry.
- The screening BP will be no greater than 160 systolic or 95 diastolic. (This limit will apply to all and any BP measurements during the screening process.)

Management Criteria during the treatment phase of the study:

- Should blood pressure rise above 165 systolic or 95 diastolic, the patient will be removed from the study.

- The subject’s hypertensive regimen may be adjusted by the primary care provider during the study as needed.

Sample size considerations:

Due to the well documented safety history of Leukine® ([1], attached as Appendix D) combined with additional patient information from the USF site, we believe that a sample size of 20 patients per research arm is adequate to assess our Primary Endpoint of measuring safety. Although the Moffitt BMT study was not specifically designed to distinguish the cognition of patients receiving GM-CSF plus G-CSF from those receiving G-CSF alone, it was possible to glean conclusions about the cognitive benefit of GM-CSF or G-CSF treatment. The study found highly significant improvement (p<0.01) in the scores of 19 patients receiving GM-CSF plus G-CSF, compared to patients receiving only G-CSF.

A Power analysis showed the following results:

Here is a table of the sample size needed per group with alpha at .20 and power at .60 for independent samples t tests:

Effect size	1 tailed test	2 tailed test
.3 - small	27	53
.5 - medium	10	20
.8 - large	4	8
1.22 – observed from BMT	3	4

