Because the effect size of cognition improvement was so high with the BMT patients, that analysis provides clinical information as a reference to choose an appropriate sample size of AD subjects to receive GM-CSF as a potential cognition enhancer (one of our Secondary Endpoints). Essentially, only 3-4 subjects are needed for a power of 0.6. Therefore, the November 15, 2013 protocol proposed to recruit a total of 40 mild-to-moderate AD patients of either sex in a placebo-controlled protocol, with 20 subjects (10 Leukine®-treated and 10 placebo) recruited at the UCD site and 20 subjects (10 Leukine®-treated and 10 placebo) recruited at the USF site. However, with the revisions from the April 6, 2016 DSMB report, the revised protocol also removes active recruiting from the USF site, due to the retirement of [name], and the remaining trial participants will be recruited at the UCD site.

The study will have two arms with subjects assigned in permuted blocks examining placebo and full recommended Leukine® dose. As mentioned above, in the trial subjects who have thus far received Leukine® at the University of South Florida, there were no serious adverse events reported by patients receiving either half dose or full dose Leukine® using the same methods proposed by this protocol. Therefore we will be starting patients at the full FDA-recommended Leukine® dose (250mcg/m²/day SC). To assure that safety concerns of treating a novel population (AD patients) with GM-CSF are addressed, initially 5 subjects will be treated for 5 days/week for 3 weeks with Leukine® and 5 participants will be given placebo, followed by a DSMB review of the CBC+diff blood data, the MRI data, and the physical exam and adverse event monitoring at the end of the treatment phase. The DSMB will then recommend whether the dosage should be continued for the subsequent 5 Leukine® treatment subjects and 5 placebo controls or whether the Leukine® should be adjusted to a half dose. Recruitment and treatment initiation will be timed to allow for the DSMB interim assessments before further patients are treated, thus assuring maximum early knowledge of any safety concerns. Up to an additional 30 patients will be recruited at each study site, assuming that some screen failures and dropouts will occur, which will still allow us to treat 20 subjects with Leukine® and 20 with placebo, combined for a total of 40 mild-to-moderate AD subjects enrolled from both the UCD and the USF sites.

Data Analysis Plan:

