Primary Endpoint: Generally, descriptive statistics will be utilized to examine safety of participants who received Leukine® injections compared to placebo injections. Safety will be assessed by measuring the toxicity grades of AE’s. These toxicity grades have been standardized by the

National Cancer Institute (NCI) Common Toxicity Criteria for Adverse Events (CTCAE Version 4.03 attached as Appendix E). Differences in toxicity grades will be compared between treatments using a Wilcoxon test for ordered outcome.

Secondary Endpoint and Exploratory Aim 1: Neuropsychological assessments will be graded and scored using the standardized scoring methods associated with each of the neuropsychological tests. Our primary measures for cognitive assessments will be based on the participants' MMSE total score and ADAS-cog total scores. All other neuropsychometry tests will be used secondarily to examine changes in specific cognitive domains. Due to the multitude of both the neuropsychometry tests and the different time points these tests are administered, a Bonferroi correction method will be used to counteract the problem of multiple comparisons.

Tertiary Endpoint: Medial Temporal Lobe Atrophy (MTA) will be assessed using an automated rating system to grade the severity of atrophy in the entire medial temporal region will be employed using the FreeSurfer software automated rating system of individual medial temporal structures, i.e., the Hippocampus (HPC), Entorhinal cortex (ERC) and Perirhinal cortex (PRC), which are specific regions of interest (ROI) in AD pathogenesis. FreeSurfer automatically computes cortical reconstruction and volumetric segmentation, including segmentation of the subcortical white matter and deep gray matter volumetric structures [34] and parcellation of the cortical surface [35] according to a previously published parcellation scheme [36]. This labels cortical sulci and gyri, and thickness values are calculated in the ROIs.

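### Lists of DSMB data leave out the vital signs the board asked for and conflict with the all-data statements, and no between-arm blood-pressure comparison is prespecified, so a rise below the removal limit could go undetected

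*Combined protocol and SAP*

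**What the plan says.** **What the DSMB asked for.** Recommendation 3, reported under Trial History, asks that all future scheduled reviews include "1) all vital sign data for each participant, 2) location of injection sites for each treatment", the recorded injection-site outcomes, and a table of treatment dates.

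**What the protocol says the DSMB sees.** Sample size considerations itemises the data behind the decision to continue or halve the dose: "followed by a DSMB review of the CBC+diff blood data, the MRI data, and the physical exam and adverse event monitoring". The Data Safety Monitoring Plan separately names laboratory results, MRI and cognitive assessments. The list of data to be monitored and reported to or by the DSMB is a list of side effects. It includes injection-site irritation but not blood pressure or hypertension. Against these, Specific Aim 1 says the board reviews all available data after each group of ten, and the DSMB and Frequency sections say all data.

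**Blood pressure on treatment.** "Vital signs, injection site review, and adverse event monitoring will be performed at each treatment visit" (Specific Aim 1). The treatment-phase criteria state "Should blood pressure rise above 165 systolic or 95 diastolic, the patient will be removed from the study", and that the subject's "hypertensive regimen may be adjusted by the primary care provider during the study as needed". For a participant found to have uncontrolled hypertension, "the DSMB will be immediately notified, adverse events reporting protocols will be followed".

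**What is analysed.** The Primary Endpoint paragraph of the Data Analysis Plan promises descriptive safety statistics in general terms, assesses safety by adverse-event toxicity grade, and adds: "Differences in toxicity grades will be compared between treatments using a Wilcoxon test for ordered outcome". It names no blood-pressure variable. The Important Note at the end of the plan lists t-tests and other tests that may be used, without assigning any of them to blood pressure.

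**The concern.** Blood pressure is important enough in this protocol to have a numeric on-treatment removal limit, written after the DSMB asked for one. Yet the board's request to see the readings is not carried into any list of what it will see, and the readings have no planned analysis.

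The analysis gap matters because the two treatment-phase rules act on the data. Removal ends a participant's series at the first high reading. Regimen adjustment can bring pressure down before a reading crosses the limit. Both reduce what a table of graded events can show. A moderate shift in the mean could leave the graded-event comparison close to null while being visible in readings the trial already holds. Safety is the primary endpoint, so this is a gap in the main question.

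**Working it through.** **1. The text side by side.**

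| Section | Data named for the DSMB | Vital signs named? |
|---|---|---|
| DSMB recommendation 3 | Vital signs, injection-site locations and outcomes, treatment dates | Yes |
| Sample size considerations | CBC with differential, MRI, physical exam, adverse events | No |
| Data Safety Monitoring Plan | Laboratory results, MRI, cognitive assessments | No |
| Data to be monitored and reported | Lists of side effects | No |
| Specific Aim 1; DSMB; Frequency | All (available) data | Implied only |

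No section outside the reported recommendation names the requested items as DSMB review data.

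**2. The cited hypertension rates.** The removal-criteria section gives 25% on Leukine and 32% on placebo in the AML trial, and 18/53 = 34% against 18/56 = 32% in the allogeneic transplant trial. The placebo rate is 32% in both. Neither trial shows a clear excess on Leukine.

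**3. What each analysis could detect.** The plan gives no blood-pressure SD, effect or margin, and its 20 per arm for safety has no calculation behind it, so there is no stated figure to reproduce. The following is an illustration.

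Inputs from the documents: 20 per arm, 15 treatment visits, 32% placebo event rate. Assumptions: between-person SD 9-11 mmHg, visit-to-visit SD 8-10 mmHg, two-sided 0.05. An event is any of the 15 readings above a threshold set so that 32% of placebo participants have one. Regimen changes are not modelled.

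Hand check for ANCOVA on the mean of the 14 readings after Day 1, adjusted for Day 1, with no removals. With between-person variance B² and visit variance W²,

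residual variance = B² + W²/14 − B⁴/(B² + W²), and SE = √(residual variance × 2/20).

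- B = 9, W = 8: 81 + 4.57 − 6561/145 = 40.3; SE = 2.01; 6/2.01 = 2.99. Power ≈ Φ(2.99 − 2.03) = 83%.
- B = 11, W = 10: 121 + 7.14 − 14641/221 = 61.9; SE = 2.49; 6/2.49 = 2.41. Power ≈ Φ(2.41 − 2.03) = 65%.

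Simulation without removals gives 63-81% in line with this. It was then repeated with removal at the first exceedance, keeping readings up to and including that one.

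| Shift | Event tests (Fisher or Wilcoxon) | ANCOVA, readings kept up to removal |
|---|---|---|
| +6 mmHg | about 13-28% | about 52-72% |
| +3 mmHg | not needed for the point | about 17-25% |
| None | – | rejects about 4-6% |

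**4. A second set of assumptions.** Here the protocol's 165 systolic limit is used directly, with usual systolic mean 130-140, between-person SD 10-12, within-person SD 8-10, and no baseline adjustment or removals. For +10 mmHg, comparing mean pressure has 71-86% power and comparing limit crossings has 11-45%. For +5 mmHg the figures are 24-33% and 1-10%. The ordering is the same.

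**The case against.** The case on the other side has real force.

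- **The itemised list describes the initial cohort.** That cohort finished treatment in February 2016, and the DSMB's request came out of its review. Thirty participants have now been treated, so one cohort of ten remains of the planned 40. A list that was never updated does not refuse the request. This stands, and it makes the DSMB half mainly a matter of reconciling text.
- **A reader might infer that the DSMB does not see blood pressure.** The documents do not support that: three sections give the board all data, and vital signs are recorded data.
- **A reader might infer that a drug effect would be missed.** That is also too strong. Uncontrolled hypertension goes to the DSMB at once and into adverse-event reporting. Under the second set of assumptions with a +10 mmHg shift, at least one of five treated participants crosses the limit with probability about 57-99%. Even with no shift that probability is about 13-80%, so a crossing alone does not identify a drug effect.
- **A reader might infer that Leukine raises blood pressure, or that hypertension alone leads to removal.** The cited trials show no clear excess, and the stopping rules also discontinue a participant who reaches grade 3 or 4 in any category.
- **The plan does not exclude a blood-pressure comparison.** Descriptive safety statistics are promised and t-tests are permitted. This is true, but neither is tied to blood pressure, and nothing says how readings before removal are kept.
- **The 32% rate comes from other populations.** It describes AML and transplant patients, not AD outpatients screened to 160/95 or below. This stands, so the power figures are illustrative.

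**Conclusion.** The concern holds in a limited form. The DSMB text is inconsistent: the lists omit vital signs, injection-site locations and per-visit review outcomes, and treatment dates, while other sections promise all data. The primary safety analysis prespecifies no between-arm blood-pressure comparison. What could go undetected is a rise that stays below the removal limit, or one masked by regimen adjustment or removal.

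The advantage of analysing the readings depends on the size of the shift. It is substantial at +6 mmHg, but at +3 mmHg even the ANCOVA would usually miss it. These figures rest on assumed SDs and shifts, a borrowed placebo rate, and a yes/no event standing in for toxicity grade. The CTCAE grade limits are not in the supplied text, so how a given reading would be graded was not assessed. This is worth correcting because safety is the primary endpoint and the data exist. It is not evidence of a safety problem.

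**What to change.** 1. Reconcile Specific Aim 1, Sample size considerations, the Data Safety Monitoring Plan, the DSMB and Frequency sections, and the list of data to be monitored. Each scheduled review should name the items the DSMB requested: all vital signs, injection-site locations and outcomes, and treatment dates.
2. In the Primary Endpoint paragraph of the Data Analysis Plan, add a comparison by arm of on-treatment systolic and diastolic pressure, adjusted for the pre-injection Day 1 value, with a 95% CI. State that every reading up to and including one that triggers removal is kept. ANCOVA on the participant mean or a mixed model over visits would serve. Label the comparison supportive.
3. Report by arm the number of participants crossing the protocol's own limit, and the number starting or increasing antihypertensive treatment, taken from the concomitant-medication record.

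The cost is protocol wording, a little more analysis and one more safety comparison to interpret. No visits or measurements are added, and the blood-pressure limits and their management are left as they are.

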Once the results are available, if the subject continues to meet entrance criteria they will return for their baseline Day 1 (randomization) visit. This visit takes place about 1 to 4 weeks after the screen visit. At this visit, vital signs are recorded, 33 ml of blood will be drawn for a CBC with differential, a complete metabolic panel (CMP), and for biomarker assays (for example, GM-CSF, IFN- γ , IL-1 β , IL-2, IL-6, IL-8, IL-10, IL-12p70, TNF- α , Eotaxin, IP-10, MCP-1, MCP-4, MIP-1 β , TARC, P-Tau, Total Tau, and A β species), and tests of cognition, such as the MMSE, ADAS-cog, the ADCS-ADL scale, Trails A, Trails B, CDR, and the Mohs Cancellation task, are administered. The test article will then be delivered by the unblinded pharmacist, administered subcutaneously by the (blinded) study nurse or clinician, and the subject then goes home.

Subsequent injections will also be administered at the clinic. About 4 ml of blood will be drawn for CBC plus differential approximately every three days during the treatment phase to monitor for leukocytosis (see safety monitoring plan), and an additional 4 ml of blood will be drawn for CMPs once every week of the treatment phase. Vital signs, injection site review, and adverse events will be recorded at each visit. At the last treatment visit approximately three weeks later, we will record vitals, perform a physical exam, review for adverse events, administer cognitive tests and draw 33 ml blood for a CBC with differential, a CMP, and biomarker assays. A brain MRI will be done for comparison with the initial screen MRI to assess for any changes in the Medial Temporal lobe and for any incidence of vasogenic edema and microhemorrhage.

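### Cognition is to be corrected by Bonferroni; Holm's step-down keeps the same family-wise bound, never rejects less, and could replace it cheaply

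*Combined protocol and SAP*

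**What the plan says.** The Data Analysis Plan handles the secondary endpoint (Specific Aim 2) and Exploratory Aim 1 in one paragraph. It gives the reason for a correction, "Due to the multitude of both the neuropsychometry tests and the different time points these tests are administered", and then the method: "a Bonferroi correction method will be used to counteract the problem of multiple comparisons". No step-down or other refinement is named, so the single-step form is the natural reading, although the text does not say so outright.

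The same paragraph sets a lead pair: "Our primary measures for cognitive assessments will be based on the participants' MMSE total score and ADAS-cog total scores". The full battery under Study Events has seven tests: "the MMSE, ADAS-cog, the ADCS-ADL scale, Trails A, Trails B, CDR, and the Mohs Cancellation task". Specific Aim 2 places testing "at baseline and at approximately 15, 45, and 90 days after initiation", which gives three post-baseline time points.

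The plan does not state the number of comparisons, whether the lead pair forms its own family, the family-wise alpha, or the sidedness. The only alpha in the documents belongs to the table under Sample size considerations, which is computed "with alpha at .20 and power at .60 for independent samples t tests" and carries no multiplicity adjustment. The analysis plan describes no simultaneous confidence intervals.

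**The concern.** Single-step Bonferroni tests every hypothesis at alpha/m, even after some have been rejected. Holm relaxes the threshold after each rejection and keeps the same family-wise bound with no added assumption. Where one valid method never rejects less than another at the same bound, the weaker one needs a reason, and the plan gives none.

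At stake is how many of the cognitive comparisons can be declared once one has been. Hypothesis 2 names both MMSE and ADAS-cog, so whether the trial can conclude on the second scale as well as the first is a question the plan itself raises. With 20 per arm, power per comparison after correction is low at moderate effects.

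**Working it through.** **Inputs from the documents.** 20 per arm, 1:1 (Sample size considerations). Standardised effects .3, .5, .8 and 1.22, the last labelled "1.22 – observed from BMT" (same section). Two lead scales, seven tests in all, three post-baseline visits.

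**Assumptions, because the documents give no figure.** Family size m = 2 × 3 = 6 or 7 × 3 = 21; family-wise alpha .05, with .20 as a sensitivity; two-sided t-tests; correlations as listed below. The value d = 1.0 is added between the table's .8 and 1.22.

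**Step 1. The plan's own figure.** Using n per group = 2(z for alpha + z for power)²/d² at alpha .20 and power .60:
- Two-tailed: 2(1.2816 + 0.2533)² = 4.71. Dividing by d² and rounding up gives 53, 19, 8 and 4. The table has 53, 20, 8 and 4, and the noncentral t reproduces all four.
- One-tailed: 27, 10, 4 and 2, against 27, 10, 4 and 3 in the table.

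The table is reproduced to within one patient. It contains no multiplicity adjustment.

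**Step 2. What Bonferroni does to power.** Per-test alpha is .05/6 = .0083 or .05/21 = .0024; at .20 it is .0333 or .0095. Exact noncentral-t power per comparison, n = 20 per arm, d = 0.5:

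| Family-wise alpha | Unadjusted | m = 6 | m = 21 |
|---|---|---|---|
| .05 | .338 | .130 | .061 |
| .20 | .613 | .276 | .140 |

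**Step 3. The two rules.** Bonferroni rejects every p ≤ alpha/m. Holm orders the p-values and compares the j-th smallest with alpha/(m − j + 1), stopping at the first failure. For m = 6 and alpha .05 the thresholds are .0083, .0100, .0125, .0167, .0250 and .0500. The first is the Bonferroni threshold, so at least one hypothesis is rejected under Holm exactly when one is rejected under Bonferroni. Later thresholds are larger, so nothing that Bonferroni rejects is lost.

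**Step 4. Size of the gain.** Simulated share of real effects declared, n = 20 per arm, family-wise alpha .05:

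| Family and truth | d | Bonferroni | Holm | Gain (points) |
|---|---|---|---|---|
| m = 6, all six real (a) | 0.5 | 13.1% | 16.1% | 3.0 |
| m = 6, all six real (a) | 0.8 | 40.7% | 50.2% | 9.5 |
| m = 6, all six real (b) | 1.0 | 65.1% | 76.1% | 11.0 |
| m = 6, all six real (a) | 1.22 | 84.9% | 92.9% | 8.0 |
| m = 6, effect at one visit only (b) | 0.5 | 12.6% | 13.1% | 0.5 |
| m = 6, effect at one visit only (b) | 0.8 | 40.2% | 41.5% | 1.3 |
| m = 21, two main scales real (a) | 0.5 | 6.1% | 6.3% | 0.2 |
| m = 21, two main scales real (a) | 0.8 | 25.6% | 26.7% | 1.1 |
| m = 21, all real (a) | 0.5 | 6.1% | 7.1% | 1.0 |
| m = 21, all real (a) | 0.8 | 25.6% | 32.5% | 6.9 |

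(a) 20,000 trials, correlation .5 between scales and .7 between visits. (b) 8,000 trials; the d = 1.0 row uses .6 between scales and .7 between visits.

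Chance that MMSE and ADAS-cog are each significant at one visit or more (m = 6, all real, .6/.7): 45.7% against 52.2% at d = 0.8, and 72.5% against 78.5% at d = 1.0. That is a gain of about 6 points.

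At family-wise alpha .20 (m = 6, all real, .5/.7): 27.4% against 35.3% at d = 0.5, and 62.5% against 75.3% at d = 0.8.

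**Step 5. Error control and the chance of any rejection.** With all nulls true, both methods have a family-wise error of 4.0% (m = 6, alpha .05, .5/.7). With one of the two scales real at d = 1.22, the realised rate rises from 2.1% to 3.6% (correlated) or from 2.5% to 4.6% (independent), in both cases below 5%. The chance of at least one rejection is the same under either method: 37.6% at d = 0.5 and 77.2% at d = 0.8 (m = 6, all real, .5/.7).

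**The case against.** The strongest reply is that Bonferroni is valid, is named in advance, and is applied to a secondary endpoint and an exploratory aim in a pilot whose primary endpoint is safety. Preferring another valid method corrects no mistake. This stands, and it limits the point to an efficiency improvement.

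Second, the larger gains need a small family, large effects and every effect real. The plan's wording covers both the number of tests and the number of visits, under a heading that joins the secondary endpoint to Exploratory Aim 1, so 21 comparisons is a natural reading. If only the two main scales respond, the gain there is 0 to 1 point. This also stands, and is why a range is given.

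Third, the undefined family matters more than the choice of method: at d = 0.5 and alpha .05, going from 6 to 21 comparisons cuts power per test from .130 to .061, more than Holm's 3 points recover. That is correct. It does not defeat the change, because Bonferroni cannot be applied either until m and alpha are fixed.

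A reader might go further in three ways that are not supported:
- That Holm makes a cognitive finding more likely. Its first step is the Bonferroni test, so the chance of any rejection is unchanged.
- That it is free. There are no simple simultaneous intervals to match it, and realised family-wise error rises within the bound when some effects are real.
- That correlated scales and visits are what make it pay. At d = 0.8 and m = 6 the gain is 9.0 points with zero correlation and 9.3 with correlations of .6 and .7. Correlation matters at d = 0.5 (1.1 against 3.0 points), where the gain is small anyway.

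**Conclusion.** The point holds as a cheap improvement. The Bonferroni correction is not an error, and nothing in the documents suggests that it would mislead. Holm gives the same family-wise guarantee without any dependence assumption and declares at least as many effects, so there is little reason to keep the single-step form for testing.

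The benefit runs from almost nothing to about 11 points per test at family-wise alpha .05. It is at the upper end only if the family is the two lead scales at three visits, all six effects are real, and they are large (d = 0.8 to 1.0). It is about 3 points at d = 0.5, about 1 point at d = 0.8 with an effect at a single visit, 0 to 1 point at d = 0.5 to 0.8 with 21 comparisons and two responsive scales, and about 7 points at d = 0.8 if all 21 are real. The claim that the trial forfeits its ability to conclude on both scales would be too strong: the difference there is about 6 points in the favourable case.

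Family size, analysis alpha, sidedness and correlations are assumptions. That Holm rejects everything Bonferroni rejects, within the same bound, does not depend on them.

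**What to change.** In the Data Analysis Plan, under the secondary endpoint and Exploratory Aim 1, replace the Bonferroni correction with the Holm step-down adjustment for the same family of tests, and report Holm-adjusted p-values. In the same edit state:
- which scales and visits make up the family, and whether MMSE and ADAS-cog are separate from the exploratory tests;
- the family-wise alpha and the sidedness.

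Bonferroni needs these items as well, so they are not an extra cost of the change. All of it should be fixed before unblinding; a later switch would look driven by the data.

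The change needs no further patients, visits or assumptions. If simultaneous confidence intervals are added later, they would stay at the Bonferroni level and so may not match the Holm decisions exactly. The plan describes none at present, so this cost is small.
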